6. GENERAL STATISTICAL CONSIDERATIONS

6.1. General Principles

Tabulations will be used extensively to summarize the data. All continuous variables will be summarized using the following descriptive statistics: n (sample size), mean, standard deviation, median, maximum and minimum. The frequency and percentages (based on the sample size) of observed levels will be reported for all categorical measures. Missing data will be denoted by n and %. Wilson confidence intervals for binomial proportions and difference in binomial proportions will be computed for efficacy variables.

All summary tables will be structured with a column/sub-table for each treatment group (TOL-463 Vaginal Insert, Placebo) and overall (All Subjects), or each site and overall. The total population size relevant to that table/column if applicable, including any missing observations will be displayed in the tables.

Participants will be excluded from Safety Population if it is unknown whether they received at least one dose, so if they had adverse events, those events would not be included in the safety summary tables, but they will be included in the AE listings. Repeat participants are counted once in all TFLs except for the safety analyses, when a participant met safety population criteria in both enrollments, the participant will be counted twice, i.e., each enrollment will be treated distinctly in the safety summary tables.

Data listings will be provided for all data. Note that in the data listings, Subject ID is the unique subject identifier, not the Study ID used on study and dates will not be included, only Study Day.

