6.3. Analysis Populations

Safety Population: This analysis population includes all randomized participants who received at least one dose of study treatment. Participants with any evidence of dosing according to the memory aid or study IP packaging return will be included in the Safety population.

Modified Intent-to-Treat (mITT) Population: This analysis population includes all randomized participants who are evaluable (see below). If a participant was enrolled more than once, (participants are allowed to be re-enrolled under PI's discretion for scenarios such as, the first enrollment terminated due to the COVID-19 shelter in place order or became ineligible after enrollment.) only the set of data from the most recent enrollment will be included in the mITT population.

The mITT population will be used as the primary efficacy analysis population.

Per-Protocol (PP) Population: This analysis population includes all randomized participants who are evaluable, complied with the assigned IP (see section 4.4.8), and returned to the study site for the TOC visit within the specified window (Visit 4 [Window: Day 85-91]) or were followed up to their diagnosis of recurrent BV. Participants who violated any inclusion/exclusion criterion at any point during the study or engaged in receptive oral, anal, or vaginal sexual intercourse within 24 hours prior to a study visit will be excluded from the PP population. If a participant was enrolled more than once, (participants are allowed to be re-enrolled under PI's discretion for scenarios such as, the first enrollment terminated due to the COVID-19

shelter in place order or became ineligible after enrollment.) only the set of data from the most recent enrollment will be included in the PP population.

In the unlikely event of an error in randomization or IP administration (i.e., incorrect treatment), participants will be grouped by the treatment they actually received in safety analyses but will be grouped by their intended randomized assignment in efficacy analyses.

Evaluable is defined as follows:

- Negative STI tests taken at baseline (*C. trachomatis*, *N. gonorrhoeae*, or *T. vaginalis*);
- For participants 21 years of age or older, documentation of or self-report of a normal or ASCUS HPV negative Pap test prior to screening, or a Pap smear performed at screening/enrollment with normal result

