6.5. Missing Data

For primary BV recurrence endpoint:

For the mITT analysis population, the BV status of subjects whose status cannot be determined by the TOC visit (visit 4) for any reason will be considered ‘treatment failure’, including subjects who discontinued early from the study and lack of treatment effect.

For the PP analysis population, subjects whose BV status cannot be determined by the TOC visit for any reason will be excluded from the analysis.

For secondary endpoints, missing values will be further excluded from the mITT and PP populations.

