8. EFFICACY EVALUATION

8.1. Primary Efficacy Analysis

The primary efficacy endpoint for the final analysis is the proportion of subjects with recurrent BV by Test of Cure (TOC, Visit 4 window: Day 85-91) as defined in section 3.3, and in section 6.5 for missing BV status by TOC.

The number of subjects, the proportion of subjects with RBV up to and including V4 will be presented overall and by treatment group with two-sided 95% Wilson confidence interval (no continuity correction). In addition, the difference in proportions between the TOL-463 Vaginal Insert arm and the Placebo group and 95% Newcombe confidence intervals (based on the Wilson CI for the individual proportions) will be presented. See [Table 6](#).

The pseudocode to fit the above analyses is below:

```
proc freq data=dataset;
  Table treatment*cure /chisq riskdiff(Newcombe) binomial(wilson) out=output
  alpha=.05;
run;
```

The primary efficacy analysis will be performed in the mITT population ([Table 6](#)). As a sensitivity analysis, the primary endpoint will additionally be assessed among all subjects in the mITT population except those terminated early due to study disruptions from the COVID-19 pandemic ([Table 7](#)). Analysis of the primary outcome measure will be repeated in the PP analysis population (secondary analysis of primary outcome). See [Table 8](#).

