Early Discontinuation from Treatment ^d	x	xx	x	xx	x	xx
Early Termination from Study ^b	x	xx	x	xx	x	xx

^a Received Treatment includes subjects who successfully received at least one dose of study treatment. It is unknown whether subjects received at least one dose if they were terminated early before Visit 2 and a Study Product Dispensing assessment at the early termination visit could not be conducted.

^b Completed Follow-up includes subjects who remained BV suppressed and were followed-up through Visit 4 as well as subjects whose participation ended prior to Visit 4 due to a clinical BV diagnosis. Terminated Early includes subjects who terminated from the study early for reasons other than a clinical BV diagnosis.

^c A blinded case review committee reviewed subjects' data to determine treatment compliance throughout the study for each subject.

^d Subjects who discontinued treatment due to RBV are included.

Table 4: Analysis Populations by Treatment Group

Analysis Populations	Reason Subjects Excluded	TOL-463 Vaginal Insert (N=X)		Placebo (N=X)		All Subjects (N=X)	
		n	%	n	%	%	n
Eligible for Safety Analysis Population	N/A	x	xx	x	xx	x	xx
Excluded from Safety Analysis Population	Any Reason	x	xx	x	xx	x	xx
	Did not receive at least one dose of study product	x	xx	x	xx	x	xx
Eligible for Modified Intent-to-Treat Analysis (mITT) Population	N/A	x	xx	x	xx	x	xx
Excluded from for Modified Intent-to-Treat Analysis (mITT) Population	Any Reason	x	xx	x	xx	x	xx
	Positive NAAT test results at baseline for C. trachomatis, N. gonorrhoeae, or T. vaginalis	x	xx	x	xx	x	xx
	HPV Criterion ^a	x	xx	x	xx	x	xx
Eligible for Per-Protocol (PP) Analysis Population	N/A	x	xx	x	xx	x	xx
Excluded from Per-Protocol (PP) Analysis Population	Any Reason	x	xx	x	xx	x	xx
	Did not meet inclusion/exclusion criteria	x	xx	x	xx	x	xx
	Positive NAAT test results at baseline for C. trachomatis, N. gonorrhoeae, or T. vaginalis	x	xx	x	xx	x	xx
	HPV Criterion ^a	x	xx	x	xx	x	xx
	Was not compliant with study product	x	xx	x	xx	x	xx
	Did not return to study site for the TOC visit within the specified window (Visit 4, Day 85-91)	x	xx	x	xx	x	xx
	Was not followed up to the diagnosis of recurrent BV	x	xx	x	xx	x	xx

Notes: N=Number of all enrolled subjects

^a For participants 21 years of age or older, documentation of or self-report of abnormal, or ASCUS HPV Positive Pap test prior to screening, or Pap smear performed at screening/enrollment with abnormal result.

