Table 5: Distribution of Protocol Deviations by Category, Type, and Treatment Group – All Enrolled Subjects

Category	Deviation Type	TOL-463 Vaginal Insert (N=X)		Placebo (N=X)		All Subjects (N=X)	
		No. of Subj.	No. of Dev.	No. of Subj.	No. of Dev.	No. of Subj.	No. of Dev.
Eligibility/enrollment	Any type	X	X	X	X	X	X
	Did not meet inclusion criterion	X	X	X	X	X	X
	Met exclusion criterion	X	X	X	X	X	X
	ICF not signed prior to study procedures	X	X	X	X	X	X
	Other	X	X	X	X	X	X
Treatment administration schedule	Any type	X	X	X	X	X	X
	Out of window visit	X	X	X	X	X	X
	Missed visit/visit not conducted	X	X	X	X	X	X
	Missed treatment administration	X	X	X	X	X	X
	Delayed treatment administration	X	X	X	X	X	X
	Other	X	X	X	X	X	X
Follow-up visit schedule	Any type	X	X	X	X	X	X
	Out of window visit	X	X	X	X	X	X
	Missed visit/visit not conducted	X	X	X	X	X	X
	Other	X	X	X	X	X	X
Protocol procedure/assessment	Any type	X	X	X	X	X	X
	Incorrect version of ICF signed	X	X	X	X	X	X
	Swab not collected	X	X	X	X	X	X
	Urine not collected	X	X	X	X	X	X
	Other specimen not collected	X	X	X	X	X	X
	Specimen result not obtained	X	X	X	X	X	X
	Required procedure not conducted	X	X	X	X	X	X
	Required procedure done incorrectly	X	X	X	X	X	X
	Study product temperature excursion	X	X	X	X	X	X
	Specimen temperature excursion	X	X	X	X	X	X
	Other	X	X	X	X	X	X
Treatment administration	Any type	X	X	X	X	X	X
	Required procedure done incorrectly	X	X	X	X	X	X
	Study product temperature excursion	X	X	X	X	X	X
	Other	X	X	X	X	X	X
Blinding policy/procedure	Any type	X	X	X	X	X	X
	Treatment unblinded	X	X	X	X	X	X
	Other	X	X	X	X	X	X

Note: N=Number of enrolled subjects randomized to the specified treatment group

Table 6: Proportion of Subjects with Recurrent Bacterial Vaginosis by the Test of Cure Visit by Treatment Group – mITT Population

Treatment Group	Number of Subjects N	Number of Subjects with RBV n	Proportion of Subjects with RBV	Proportion of Subjects with RBV 95% CI ^a	Difference in Proportions of Subjects with RBV between Treatment Arms	Difference in Proportions of Subjects with RBV between Treatment Arms 95% CI ^b
TOL-463 Vaginal Insert	x	x	0.xx	0.xx, 0.xx	0.xx	0.xx, 0.xx
Placebo	x	x	0.xx	0.xx, 0.xx		

Notes: The denominator for proportions is based on the number of subjects enrolled in the respective treatment group.

^a 95% Wilson confidence interval for the proportion of subjects with RBV.

^b 95% Newcombe confidence interval for difference in proportions between arms.

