Table 7: Proportion of Subjects with Recurrent Bacterial Vaginosis by the Test of Cure Visit by Treatment Group – mITT Population, Excluding Subjects Terminated Early due to COVID-19

Treatment Group	Number of Subjects N ^a	Number of Subjects with RBV n	Proportion of Subjects with RBV	Proportion of Subjects with RBV 95% CI ^b	Difference in Proportions of Subjects with RBV between Treatment Arms	Difference in Proportions of Subjects with RBV between Treatment Arms 95% CI ^c
TOL-463 Vaginal Insert	x	x	0.xx	0.xx, 0.xx	0.xx	0.xx, 0.xx
Placebo	x	x	0.xx	0.xx, 0.xx		

Notes: The denominator for proportions is based on the number of subjects enrolled in the respective treatment group.

^a This analysis includes all subjects in the mITT population except those terminated early due to study disruptions resulting from shelter in place orders in response to the COVID-19 pandemic.

^b 95% Wilson confidence interval for the proportion of subjects with RBV.

^c 95% Newcombe confidence interval for difference in proportions between arms.

Table 8: Proportion of Subjects with Recurrent Bacterial Vaginosis by the Test of Cure Visit by Treatment Group – PP Population

Treatment Group	Number of Subjects N	Number of Subjects with RBV n	Proportion of Subjects with RBV	Proportion of Subjects with RBV 95% CI ^a	Difference in Proportions of Subjects with RBV between Treatment Arms	Difference in Proportions of Subjects with RBV between Treatment Arms 95% CI ^b
TOL-463 Vaginal Insert	x	x	0.xx	0.xx, 0.xx	0.xx	0.xx, 0.xx
Placebo	x	x	0.xx	0.xx, 0.xx		

Notes: The denominator for proportions is based on the number of subjects enrolled in the respective treatment group.

^a 95% Wilson confidence interval for the proportion of subjects with RBV.

^b 95% Newcombe confidence interval for difference in proportions between arms.

Table 9: Rate of Recurrent Bacterial Vaginosis by the Test of Cure Visit by Treatment Group – mITT Population

Treatment Group	Number of Subjects with RBV	Person-days	Rate of RBV	Rate of RBV 95% CI ^a
TOL-463 Vaginal Insert	x	x	0.xx	0.xx, 0.xx
Placebo	x	x	0.xx	0.xx, 0.xx

^aExact Poisson 95% confidence intervals.

Table 10: Rate of Recurrent Bacterial Vaginosis by the Test of Cure Visit by Treatment Group – PP Population

Treatment Group	Number of Subjects with RBV	Person-days	Rate of RBV	Rate of RBV 95% Cl ^a
TOL-463 Vaginal Insert	x	x	0.xx	0.xx, 0.xx
Placebo	x	x	0.xx	0.xx, 0.xx

^a Exact Poisson 95% confidence intervals.

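### The notes to SAP Tables 6, 7, 8 and 13 give enrolled women as the denominator, which contradicts the mITT and PP sets those tables are meant to report

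*SAP*

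**What the plan says.** The SAP's Preface makes the table shells part of the plan for the final analyses. One note stands under four of them: Table 6 (primary endpoint, mITT), Table 7 (mITT less COVID-19 terminations), Table 8 (PP) and Table 13 (mITT by site). It reads: "The denominator for proportions is based on the number of subjects enrolled in the respective treatment group".

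Other parts of the SAP point to smaller sets:

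- Section 8.1: "The primary efficacy analysis will be performed in the mITT population". It assigns the COVID-19 sensitivity analysis to Table 7 and the PP repeat to Table 8.
- Section 6.3, on mITT: "This analysis population includes all randomized participants who are evaluable (see below". PP is narrower still. It also requires compliance, and either a test-of-cure visit in window or follow-up to recurrence.
- Section 6.1, on table sizes: "The total population size relevant to that table/column if applicable, including any missing observations will be displayed in the tables".
- Table 7, footnote to its N column: "This analysis includes all subjects in the mITT population except those terminated early due to study disruptions".
- Section 6.5, on missing outcomes in mITT: "the BV status of subjects whose status cannot be determined by the TOC visit (visit 4) for any reason will be considered" treatment failure. For PP: "For the PP analysis population, subjects whose BV status cannot be determined by the TOC visit for any reason will be excluded from the analysis".

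**The concern.** Table 6 carries the primary result, and its note states a denominator that the rest of the plan does not use. The mITT and PP sets are subsets of the randomized women. A programmer or reader who takes the note at its word would divide by too large a number. If the count of recurrences still came from the analysis set, women outside the set would in effect be counted as free of recurrence. The proportions, their Wilson intervals and the Newcombe interval for the difference would all be affected. If the note is ignored, the report still carries a false description of its primary denominator.

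**Working it through.** **1. Is 'enrolled' shorthand for the analysis set?** No.

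- Table 4 says "Notes: N=Number of all enrolled subjects" and then tabulates why enrolled women fall outside mITT and PP.
- Tables 11, 12 and 14 to 18 name mITT or PP in their notes.
- Tables 27 and 36 use the same denominator sentence but change the population to women who used at least one insert, which matches their Safety set. The sentence is thus a population-specific rule, and in four tables it names the wrong population.

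**2. The plan's own figures (SAP Section 5; test from Protocol Section 10.1).** Inputs: 40% vs 20%, 1:1 allocation, 200 evaluable, two-sided 5% chi-square, 80% of enrolled evaluable.

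- Enrollment: 200 / 0.80 = 250, so 125 enrolled and 100 evaluable per arm. This agrees with the plan.
- Power at 100 per arm: Φ[(0.20√100 − 1.96√(2 × 0.30 × 0.70)) / √(0.40 × 0.60 + 0.20 × 0.80)] = Φ(1.15) = 0.876. This agrees with the stated minimum of 85%.

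**3. The note followed with an analysis-set numerator.** Let x be recurrences in the set, n the size of the set, E the number enrolled in the arm, and f = n/E. The printed proportion is x/E = (x/n)(n/E) = p × f. With the same f in both arms, the difference is also multiplied by f. The documents give no actual share, so f is an assumed range:

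| f | Placebo (0.40 × f) | TOL-463 (0.20 × f) | Difference, points |
|---|---|---|---|
| 1.00 | 40% | 20% | 20 |
| 0.98 | 39.2% | 19.6% | 19.6 |
| 0.95 | 38% | 19% | 19 |
| 0.90 | 36% | 18% | 18 |
| 0.80 | 32% | 16% | 16 |
| 0.70 | 28% | 14% | 14 |
| 0.60 | 24% | 12% | 12 |

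**4. Full output at f = 0.80.**

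- Analysis-set denominator: TOL-463 20/100 = 0.20 (Wilson 0.13, 0.29); placebo 40/100 = 0.40 (0.31, 0.50). Difference −0.20 (Newcombe −0.32, −0.07); chi-square 9.52, p = 0.002.
- Enrolled denominator: TOL-463 20/125 = 0.16 (0.11, 0.23); placebo 40/125 = 0.32 (0.24, 0.41). Difference −0.16 (−0.26, −0.05); chi-square 8.77, p = 0.003.

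**5. Unequal shares by arm.**

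- TOL-463 0.85, placebo 0.75: 0.40 × 0.75 − 0.20 × 0.85 = 0.30 − 0.17 = 13 points.
- TOL-463 0.70, placebo 0.90: 0.36 − 0.14 = 22 points.

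Both proportions fall whenever any enrolled woman in the arm is outside the set, but the difference may shrink or grow.

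**6. Which tables are exposed.**

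- *Table 6.* Undetermined outcomes stay in mITT as failures. Exclusions come only from baseline STI results, Pap results and superseded enrollments, and a positive STI test is already an exclusion reviewed before enrollment (SAP Section 4.3.2.1). The share is plausibly near 1.
- *Table 7.* On this reading, women removed because of COVID-19 would return to the denominator as non-recurrent, although Table 6 counts those of undetermined status as failures.
- *Table 8.* Exclusions for compliance, visit window and undetermined status make PP smaller, and these can differ by arm.

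**The case against.** The strongest reply is that the plan's body already settles the denominator. Section 6.3 makes mITT the primary efficacy population, Section 8.1 applies it, each title names its set, and each shell has an N column. The single PROC FREQ call in Section 8.1, run on the mITT or PP dataset, divides by that dataset's size and gives the right intervals. This stands: the arithmetic error arises only if someone follows the note against the body.

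The multiplication by f also needs an enrolled denominator paired with an analysis-set numerator. A programmer who used all enrolled women for both would produce an all-enrolled analysis, not a systematic deflation. This also stands.

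A reader might infer that the plan will understate the primary result by one fifth, since the SAP assumes 80% evaluable. The documents do not support that. SAP Section 4.1 ties the 200 evaluable women to the test-of-cure visit, so the 80% plausibly allows for dropout, and Section 6.5 keeps women with undetermined outcomes in mITT. Even at 80%, the p-value moves only from 0.002 to 0.003. A reader might also infer that Table 13 would divide each site's count by the whole arm. That is strained, because each site block has its own N and the note is naturally read within the block.

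What the reply does not remove is the contradiction itself. If the body prevails, the primary table is issued with an incorrect note.

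**Conclusion.** The inconsistency is real and sits under the primary table. The four notes are wrong as written, and the titles, Sections 6.1, 6.3 and 8.1, and Table 7's footnote show what was intended. This is a consistency error in the shells; the choice of analysis set is not in doubt.

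The numerical risk is conditional. It requires the note to be followed with analysis-set numerators, and its size depends on a share the documents do not report. At an assumed 95% the planned difference goes from 20 to 19 points, and at 80% to 16. For Table 6 the lower end of that effect is the more plausible. For Table 8 the effect could be larger and its direction on the difference is not fixed: an assumed 60% in both arms gives 12 points, and unequal shares can push the difference above 20. The stronger conclusion, that the plan as a whole would deflate the primary estimate, does not follow.

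**What to change.** Replace the note in the four shells with: *Denominator = number of subjects in the stated analysis population (column N) in that treatment group*. Name the population in each:

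- Table 6: mITT.
- Table 7: mITT less COVID-19 terminations.
- Table 8: PP.
- Table 13: mITT at that site.

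The cost is four table notes. No data, code, test or population definition changes. The correction is best made before the tables are programmed, so that the note and the Section 8.1 code agree.
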